3.2. Study Outcome Measures

3.2.1. Primary

To measure **drug efficacy** as per standard parasitological endpoints including a) Cure Rate as defined by the proportion of children who have zero eggs per gram of stool as assessed by Kato-Katz four weeks following treatment and b) Egg reduction Rate as defined by the percent reduction in egg burden from baseline to four weeks post treatment as assessed by Kato-Katz.

3.2.2. Secondary

[figure not shown]
- 3.2.2.1. To assess novel antigenic endpoints (CCA and CAA) in all children and in relation to PK/PD parameters associated with cure (Area-Under-the Curve (AUC)) at 4 +/- 1 weeks post-PZQ in a sub-set of children.
- 3.2.2.2. To monitor adverse events in children for 12 hours post-PZQ dosing.
- 3.2.2.3. To assess bone marrow, renal, and liver toxicity as captured before dosing and 12 hours after.
- 3.2.2.4. To measure iron status, hemoglobin, and age and gender adjusted longitudinal growth and nutritional status at different varying doses and dosing intervals (every six or 12 months)
- 3.2.2.5. To evaluate the mechanisms mediating the effect of varying treatment doses and frequencies on growth and nutritional morbidity including measures of Environmental Enteric Dysfunction (EED) and inflammation (fecal calprotectin, urine lactulose:mannitol ratio, serum endotoxin, serum endotoxin core antibody, and pro-inflammatory cytokines).
- 3.2.2.6. To evaluate inter-individual variability in PZQ AUC as modified by EED
- 3.2.2.7 To assess immune responses to *S. mansoni* infection and treatment
- 3.2.2.8 To quantify the prevalence and evaluate the pattern of schistosomiasis-related morbidity as determined by ultrasound

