3.1.2. Secondary

To assess the **safety and** efficacy and PK/PD of PZQ administered at different dose regimens.

- 3.1.2.1. To evaluate the PK/PD of both PZQ enantiomers given the concern that this has varied in studies of *S. mansoni*.
- 3.1.2.2. To expand PD endpoints for drug efficacy to include state-of-the art antigen tests to accurately capture residual worm burden (Circulating Cathodic and Anodic Antigens (CCA and CAA)).
- 3.1.2.3. To assess the safety and impact of PZQ treatment (dose and interval) on key measures of morbidity 6 and 12 months after initial treatment and mechanisms mediating morbidity
- 3.1.2.4. To further evaluate the safety of higher PZQ dosing (80 mg/kg) including bone marrow, renal, and liver toxicity as captured before dosing and 12 hours after.
- 3.1.2.5. To evaluate the impact of different doses (40 vs. 80 mg/kg) and varying dosing intervals (every 6 or 12 months) on iron status, hemoglobin, and age and gender adjusted longitudinal growth and nutritional status as captured by height and weight for age, and weight for height z-scores as determined by WHO Anthro.
- 3.1.2.6. To evaluate the mechanistic role of *Environmental Enteric Dysfunction (EED)* in the pathogenesis of schistosomiasis related morbidities. We will capture state of the art biomarkers of EE including fecal calprotectin, urine lactulose:mannitol ratio, serum

endotoxin, serum endotoxin core antibody, and pro- inflammatory cytokines and employ Path Modeling techniques to identify mechanistic pathways.

- 3.1.2.7. To assess the role of Environmental Enteric Dysfunction (EED) in inter-individual variability in PZQ area under the curve (AUC) PK parameters demonstrated in this age group.
- 3.1.2.8. To explore immune responses to *S. mansoni* infection and treatment
- 3.1.2.9. To assess the prevalence and the pattern of schistosomiasis-related morbidity as determined by ultrasound scan.

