To test gut permeability and absorptive capacity, lactulose-mannitol solution (containing 250 mg/mL lactulose and 50 mg/mL mannitol in purified water) will be administered to study participants orally at a

dose of 2ml/kg up to a maximum of 20 ml. Prior to administration of the solution, the child will be fasted for 30 minutes. Breast feeding will continue. A urine bag will be strapped to ensure all the urine is collected. The first urine sample voided will be considered as baseline. A new bag will then be put in place to continue urine collection for 2 hours. Once collected, an aliquot of 2 ml of urine will be stored between 2°C and 8°C having added 2 drops of chlorhexidine. Two hours after ingestion of LM solution, the test will be stopped. If the child has not passed any urine, the test time will be extended until the next urine is voided.

Following the LM test, two doses of PZQ will be administered three hours apart. After receiving praziquantel, all children will stay at the study premises for 3-6 hours with a guardian monitoring side effects. After administration of the second dose of the study product, children will undergo ultrasound scan to determine presence or absence of any pathology related to schistosomiasis. The Niamey Protocol will be used to grade severity of disease.

The subset of children (approximately N=150) who will be randomly selected for PK sampling (four blood draws in total) children will stay at the premises for at least 6 – 8 hours after administration of the initial dose of praziquantel. At the time of discharge, children who will be found to be infected with soil-transmitted helminths will be treated with albendazole 200 mg (12 – 24 month old children) or albendazole 400 mg (children over age two). Blood Chemistry to ascertain renal and liver function will be repeated 6 – 8 hours after administration of the first dose of praziquantel, before discharge.

2. *Study Visit 2.* Stool will be collected 4 weeks (+/- 1 week) after treatment. Two stools will be collected on consecutive days to quantify egg counts by Kato Katz. Field workers will be responsible for picking up cups at this timepoint. No visit to the field laboratories will be required. Urine will be collected for CCA/CAA. Blood (7 ml) will be collected for the same subset of N=150 subjects for studies of immunological responses as at baseline.

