7.3. Laboratory Based Screening, Enrollment/Baseline

Philippines site: If children are deemed eligible based on both screening phases, they will be “admitted” to the Palo Field Laboratory for 12 hours. There will be one medical technologist assigned to four children.

Uganda site: If children are deemed eligible based on both screening phases, they will be “admitted” to the Kabatereine Schistosomiasis Research Center in Buliisa District for 12 hours. There will be one nurse assigned to four children. Technical work in this phase will be performed by Ministry of Health personnel (Vector Control Division).

Phase two screening will take place at the field laboratories to ensure other inclusion/exclusion criteria are met prior to enrollment. Specifically, information will be provided which will detail the second phase of screening as well as the full procedures, and informed consent obtained. Phase two screening includes capture of weight and height to determine nutritional status (weight for height z-score), laboratory studies

to rule out severe anemia, physical examination and history to rule out a chronic medical condition that might make deem a child ineligible.

At both sites, the following activities will take place in **ALL** participants:

- History and physical exam
- Weight and height
- A catheter will be placed for blood draws
- Blood collection (5 mL) for complete blood count (CBC) and renal/liver toxicity measures. Serum will also be used for morbidity studies (EED biomarkers, iron biomarkers, and pro-inflammatory cytokines). Before discharge, another blood sample will be removed between 6 – hours after administration of the first dose of the study drug. This enables monitoring for possible toxicity.
- HIV testing and malaria testing
- Lactulose/Mannitol beverage. Children will take a small volume of a lactulose/mannitol at a dose of 2 ml/kg up to a maximum of 20 ml beverage as a measure of gut permeability and gut absorptive capacity and we will collect urine for 2 hours afterwards. They will fast 30 minutes before the lactulose:mannitol administration.
- Ultrasound scan for detection of schistosomiasis-related morbidity.
- **Stool** collection for parasitology by Kato-Katz if two stools not provided prior to enrollment, fecal calprotectin and fecal occult blood (performed on site).
- **PZQ** administration at the study assigned dose after a meal consisting of local foods.

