- Final blood collection (3 ml) for CBC, renal, and liver toxicity 12 hours post dosing (all participants)

To participants further randomly selected for pharmacokinetics and immunology sub-studies:

- At each site participants will be randomly allocated into two groups with different blood sampling frequency but similar overall volume (an extra 5 ml)
 - Pharmacokinetic sub-study:
 - In a sub-set of children (N= 150 in both sites) the indwelling cannula will be used to obtain four blood samples of approximately 1 ml for PK/PD studies at respective intervals. Participants who will be sampled for PK/PD studies **will not** participate in the immunology sub-study
 - Immunology sub-study:

- In a sub-set of children in Uganda, 7 ml of whole blood will be collected for immunology assays (such as flow cytometry, Luminex, ELISpot and ELISA).
- Participants who will be sampled for the immunology sub-study **will not** participate in the PK/PD study
- A subset of children without schistosomiasis will be recruited and will provide urine before and after ingesting lactulose-mannitol solution. Stool and 4ml of blood will also be taken for study of gut microbiota/EED biomarkers and morbidity markers.

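### The laboratory-toxicity endpoint has conflicting draw times, tests and lengths of stay, no named reference administration, and no prespecified 80 v 40 mg/kg comparison

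*Combined protocol and SAP*

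**What the plan says.** **Endpoint.** Objective 3.1.2.4 concerns the safety of 80 mg/kg, including "bone marrow, renal, and liver toxicity as captured before dosing and 12 hours after". Outcome 3.2.2.3 repeats the time point: "To assess bone marrow, renal, and liver toxicity as captured before dosing and 12 hours after".

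**Section 4.2.1, Study visit 1/Baseline.** Here "two doses of PZQ will be administered three hours apart". Renal and liver chemistry "will be repeated 6 – 8 hours after administration of the first dose of praziquantel, before discharge". No repeat CBC is named. On length of stay, "all children will stay at the study premises for 3-6 hours with a guardian monitoring side effects"; the pharmacokinetic subset stays at least 6-8 hours after the initial dose.

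**Section 7.3.** Children are admitted at each site for 12 hours; for the Philippines the text is "to the Palo Field Laboratory for 12 hours". Two post-dose draws are listed for all participants. Before discharge, "another blood sample will be removed between 6 – hours after administration of the first dose of the study drug", with no upper limit in the text. Later in the list comes "Final blood collection (3 ml) for CBC, renal, and liver toxicity 12 hours post dosing (all participants".

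**Sections 11.1 and 11.4.** The only safety hypotheses concern adverse events within 3 hours of dosing. Section 11.4 plans chi-squared tests of adverse-event prevalence and tabulations of rare events and severity. Haemoglobin and anaemia appear in 11.1 only as 12-month morbidity outcomes.

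**The concern.** Section 2.3.1 names exposure to the higher dose as the primary risk in a vulnerable population, and objective 3.1.2.4 makes laboratory safety at 80 mg/kg a separate aim. The dose groups differ at baseline only in what is given at hour 3, so the time since that second administration determines how long the extra drug has had to act when blood is drawn.

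Two sites following different sections would measure different endpoints, and one of them would have no post-dose CBC, hence no bone marrow measure. Even with consistent samples, the plan does not say how they answer the 80 v 40 mg/kg question.

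**Working it through.** No sample size or power figure underlies this endpoint, so there is none to reproduce. The check sets the sections side by side and does clock arithmetic on their stated times.

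**1. The instructions compared (baseline visit)**

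| Place | Post-dose draw | Clock starts at | Tests | Stay |
|---|---|---|---|---|
| 3.1.2.4, 3.2.2.3 | 12 h | not stated | marrow, renal, liver | not stated |
| 4.2.1 | 6-8 h | first dose | renal and liver chemistry | 3-6 h; PK subset at least 6-8 h |
| 7.3, pre-discharge draw | from 6 h, upper limit absent | first dose | not itemised | 12 h |
| 7.3, final draw | 12 h | not stated | CBC, renal, liver | 12 h |

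Sections 2.3.1 and 9.4 also give 12 hours of observation at enrolment.

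**2. Time since the second administration.** Input: a 3 h interval (4.2.1). Formula: hours after second = hours after first − 3.

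- Section 4.2.1 draw: 6 − 3 = 3 h to 8 − 3 = 5 h.
- 12 h counted from the first administration: 12 − 3 = 9 h.
- 12 h counted from the second: 12 h, which is 12 + 3 = 15 h after the first.

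**3. Can the 12-hour draw be taken within the section 4.2.1 stay?** Counted from the first administration, a 3-6 h stay ends at hour 3-6. Counted from the second, it ends at hour 3 + 3 = 6 to 3 + 6 = 9. The latest end, hour 9, is 12 − 9 = 3 h before the earliest reading of the 12-hour draw. On the first-administration clock, even the 6-8 h draw in the same section starts only as the stay ends. For the PK subset, 6-8 h is a minimum: it does not rule out a 12-hour draw, but does not provide for one.

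**4. Do the adverse-event hypotheses reach these values?** The 3-hour window in 11.1 closes at hour 3 (from the first administration) or hour 3 + 3 = 6 (from the second). A 12-hour value is outside on either count. A 6-8 h value at most touches the edge, at hour 6.

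**5. The six-month visit.** Section 7.5 describes a visit of about three hours but lists a draw from 6 h after the first dose; 3 is less than 6. Section 9.4 expects discharge 3-4 h after dosing. Counted from the second administration, that is hour 6-7, which could contain the draw but not within a three-hour visit. Section 9.1 has monitoring for 12 h after every administration. These three sections also disagree.

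**The case against.** The strongest reply is that section 4.2.1 is the outlier. The 12-hour time point appears in the objective, the outcome and the 7.3 procedure list, and the 12-hour stay in 2.3.1, 7.3 and 9.4. Section 4.2.1 may simply be outdated narrative, or an earlier chemistry draw and a final 12-hour panel may both be intended. This stands in part. A reader of 4.2.1 alone might infer that no 12-hour sample or post-dose CBC is planned; section 7.3 shows otherwise. The fault is conflicting instructions. If two draws are intended, nothing says which is the endpoint, and the 4.2.1 stay still cannot hold the 12-hour one.

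A second reply is that laboratory toxicity is not absent from the analysis. The adverse-event definition in 9.2.1 includes abnormal laboratory findings, 11.4 compares and tabulates adverse events by arm without repeating the 3-hour limit, the DSMB may see laboratory values (9.6.2), and 11.4 defers full details to a later SAP. This also stands in part: abnormal values could enter the 11.4 tables indirectly. But the 11.1 hypotheses stop at 3 hours, halting rule 2 in 9.5 excludes laboratory-defined events, and DSMB review is not a between-dose estimate. A later SAP can add an analysis but cannot recover a sample that was not drawn.

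A reader might also infer that the earlier draw biases the comparison towards no toxicity, or costs a calculable amount of power. The documents do not support either. They give no abnormality rates or onset times, and section 11.2 does not size the trial on this endpoint. An earlier draw would understate a dose difference only if abnormalities are still accruing 3-5 hours after the second administration, which the documents do not establish.

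**Conclusion.** The concern holds as an inconsistency and an omission. Post-dose laboratory toxicity is placed 3-5 hours after the second administration in one section and 9 or 12 hours after it in others, with different tests and lengths of stay. A site following section 4.2.1 would not obtain the stated endpoint: the CBC is not named there, and outside the PK subset the stay ends at least 3 hours too soon. No dedicated 80 v 40 mg/kg laboratory comparison is prespecified.

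This rests only on the stated times and the three-hour interval. No effect on bias or power is claimed. The consequence is that objective 3.1.2.4 could be answered with different endpoints at different sites, or without a planned estimate.

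**What to change.** 1. Reconcile 3.1.2.4, 3.2.2.3, 4.2.1 and 7.3 on draw time, the administration that starts the clock, the tests repeated and the length of stay. Do the same for the six-month visit across 7.5, 9.1 and 9.4. This review takes no position on which schedule is right.
2. State which draw is the endpoint, and record actual administration and sampling times.
3. In 11.1 and 11.4, add a laboratory-toxicity summary by baseline dose at that draw. One adequate form is change, or grade shift, from the pre-dose value, with a between-dose difference and 95% confidence interval.

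The cost is protocol wording and a few extra safety tables. The draws concerned are already listed in 7.3.

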4. STUDY DESIGN

4.1 Trial design

Four arm randomized double blind placebo-controlled trial with a 4 week, 6 months and 12 month follow up (Figure I). Half of the cohort will receive an additional PZQ dose (at the same dose given at baseline) at 6 months and half placebo. Parasitological endpoints will be measured at 4 weeks and at 6 months urine stored for future antigen testing. Morbidity endpoints will be assessed at 6 and 12 months.

Figure I Schematic of Study Design

4.2 Study population

4.2.1 PSAC with Schistosomiasis

We will recruit approximately 600 children aged 12 to 47 months inclusive at two field sites with approximately N=300 at each site. Subjects will be recruited from *S. japonicum* endemic rice farming villages in The Philippines and *S. mansoni* endemic villages along Lake Albert, Uganda. In

Uganda, the prevalence of infection in children is very high in the proposed villages along Lake Albert, where a recent study led by co-PI [name] found a prevalence of 57% by Kato -Katz among children aged 3-5 years.¹³ In a community survey conducted as part an NIH funded study in May of 2016 at the proposed site in Leyte, The Philippines, the prevalence of infection among individuals ages 7-30 was 51.9%. The community survey was extended to include an assessment of the prevalence of infection among children ages 1-4 and was found to be 42%. This high prevalence is likely due to the fact that young children had not been included in annual preventive chemotherapy campaigns.

Given the population size per village ranges from approximately 578 to 1878 individuals at both sites, about 10% of the population is under four (57-187 per village) and we expect the prevalence of schistosomiasis in young children can conservatively be estimated at 40%, (23-75 infected children under four per village), we will need to recruit in 15-20 villages across the two sites which is entirely feasible. The investigative teams have worked in the proposed villages, including numerous studies involving children, and communities have always participated without concern.

In addition, the general health of children in both study areas is poor. In our recent studies from The Philippines, 31.7% of subjects aged 8-30 were anemic; of these, anemia of inflammation was the primary cause among 67%.¹⁴ In addition, 67.1% of children were chronically under-nourished as assessed by HAZ < -2 and 14.9% were wasted as captured by BMI-Z.¹⁵ Importantly, we expect these prevalences to be higher among children under four who disproportionately bear the burden of these morbidities in the LMIC setting. The under-five population in the Lake Albert region of Uganda also experiences high rates of undernutrition with approximately 38% stunted and 16% underweight.¹⁶ Thus, we expect there to be variability in the morbidity outcomes assessed such that treatment may be impactful and mechanisms mediating them captured.

Trial Phase: II multicenter (two centers)

Study Arms: The study will have four arms as follows:

Arm 1: 40 mg/kg dose at baseline & Placebo 3 hours later//Placebo & Placebo 3 hours later at six months post baseline (N = 150). N=75 will be recruited in this arm at each site.

Arm 2: 40 mg/kg dose at baseline & Placebo 3 hours later //40 mg/kg dose & Placebo 3 hours later at six months post baseline (N = 150). N=75 will be recruited in this arm at each site.

Arm 3: 80 mg/kg dose split at baseline as 40 mg/kg and 40 mg/kg 3 hours later// Placebo & Placebo 3 hours later at six months post baseline (N = 150). N=75 will be recruited in this arm at each site.

Arm 4: 80 mg/kg dose at baseline split as 40 mg/kg and 40 mg/kg 3 hours later //80 mg/kg dose split as 40 mg/kg and 40 mg/kg 3 hours later at six months post baseline (N = 150). N=75 will be recruited in this arm at each site.

Study Enrollment timeline: Subject screening and recruitment will occur over 24 months.

Duration of participation: Individual subject participation will be approximately 13 months

Study agent and administration: For study agent conformity and quality, we will obtain PZQ tablets from a single source, Macleods Pharmaceuticals. Children will be randomized and receive either 40 mg/kg or 80 mg/kg (split as 2 doses of 40 mg/kg over 3 hours) at baseline. Children randomized to the 40 mg/kg arm will receive placebo 3 hours post treatment while children randomized to the 80 mg/kg arm will receive two split doses of 40 mg/kg over 3 hours. At the six months post initial treatment time point, children will be randomized to receive the same dose as they received at baseline or to receive placebo. The research pharmacy, *Tedor Pharma, Cumberland, RI*, will compound a placebo tablet matched for the active agent's excipients, color, shape, and size.

The research pharmacy, International AIDS Vaccine Initiative (IAVI) pharmacy will allocate the study agent and placebo into pre-labelled vials. The vials will be pre-labelled with the study name, “investigational use only”, the study ID, and either A, B, C, or D to denote first and second doses at baseline or 6 months as per Table I below. Prior to study initiation, the study biostatistician, [name], will share the randomization code with IAVI. Using this, they will fill each vial with 3 tablets of either Praziquantel or Placebo based on the study ID assignment. This allows sufficient dose for the range of weights expected and in case of vomiting within an hour of dose with a need to repeat. This includes reference to both the study timepoint and whether it is the first or second dose at that timepoint as a subject may, for example, receive praziquantel for the first dose and placebo for the second dose at baseline OR praziquantel for both doses based on his/her randomization status.

Table I

| Baseline Visit | Study Drug Vial Letter |
|-------------------|------------------------|
| Dose 1 | A |
| Dose 2 | B |
| Visit at 6 months | |
| Dose 1 | C |
| Dose 2 | D |

For both arms, we will crush the study agent and give with juice as per the Ugandan and other studies.^{7,17} This will be a quasi-double blind approach as we will not be able to fully mask taste for participants. About 30 minutes prior to dose administration, a meal consisting of local foods will be provided as this increases PZQ bioavailability.

Trial periods/timepoints:

1. *Screening* We propose to employ a two stage screening process. The first phase is a village - based survey to identify children who are infected using rapid point of care testing (urine Circulating Cathodic Antigen (CCA)). CCA provides a highly sensitive and efficient means to screen children, with high sensitivity demonstrated in young children.^{18,19 20,21} Two stool samples (taken on consecutive days) will also be collected from every child who is CCA positive prior to the start of the study, at four weeks +/-1 week after treatment, and at 12 months post-treatment to provide a measure of infection intensity. Fecal smears will be prepared from each sample in duplicate applying the thick Kato-Katz technique for the detection of *S. mansoni*, *S. japonicum* and soil-transmitted helminths. Mean egg counts per gram of stool (epg) will subsequently be calculated and three intensity categories will be considered for *S. mansoni* and *S. japonicum* infection: light (1-99 epg), medium (100 – 399 epg) and heavy (>400 epg) as per World Health Organization Guidelines.²²

The second phase of screening will occur at the field laboratories in Palo, Leyte, The Philippines and in Lake Albert, Uganda. Prior to study enrollment, each child will undergo a physical exam and medical history to determine eligibility. Children who are not eligible based on severe malnutrition (WHZ < -3.0), severe anemia (hemoglobin < 7.0 g/dL) or chronic medical condition as defined by a disease lasting longer than three months and impacting a child's daily function or normal activities will be excluded at this stage.²³

1. *Study visit 1/Baseline.* After determination of eligibility, subjects will be enrolled following all screening assessments. Both field stations have a patient intake area with private areas for consenting and physical examinations. At this visit, a small blood drawing catheter will be placed to minimize the number of times children need to have a needle stick. Blood will be drawn for baseline morbidity studies (5 ml). In depth measures of nutritional status will be made, and children will be randomized to receive either 40 mg/kg or 80 mg/kg of Praziquantel either annually or six-monthly (4 arms).

In addition, children will be randomly split into two groups, half will have an extra 7 ml of blood drawn at the time of the morbidity studies (N=150) for immunologic studies and half will take part in pharmacokinetic studies (N=150, further details below).

To test gut permeability and absorptive capacity, lactulose-mannitol solution (containing 250 mg/mL lactulose and 50 mg/mL mannitol in purified water) will be administered to study participants orally at a

dose of 2ml/kg up to a maximum of 20 ml. Prior to administration of the solution, the child will be fasted for 30 minutes. Breast feeding will continue. A urine bag will be strapped to ensure all the urine is collected. The first urine sample voided will be considered as baseline. A new bag will then be put in place to continue urine collection for 2 hours. Once collected, an aliquot of 2 ml of urine will be stored between 2°C and 8°C having added 2 drops of chlorhexidine. Two hours after ingestion of LM solution, the test will be stopped. If the child has not passed any urine, the test time will be extended until the next urine is voided.

Following the LM test, two doses of PZQ will be administered three hours apart. After receiving praziquantel, all children will stay at the study premises for 3-6 hours with a guardian monitoring side effects. After administration of the second dose of the study product, children will undergo ultrasound scan to determine presence or absence of any pathology related to schistosomiasis. The Niamey Protocol will be used to grade severity of disease.

The subset of children (approximately N=150) who will be randomly selected for PK sampling (four blood draws in total) children will stay at the premises for at least 6 – 8 hours after administration of the initial dose of praziquantel. At the time of discharge, children who will be found to be infected with soil-transmitted helminths will be treated with albendazole 200 mg (12 – 24 month old children) or albendazole 400 mg (children over age two). Blood Chemistry to ascertain renal and liver function will be repeated 6 – 8 hours after administration of the first dose of praziquantel, before discharge.

2. *Study Visit 2.* Stool will be collected 4 weeks (+/- 1 week) after treatment. Two stools will be collected on consecutive days to quantify egg counts by Kato Katz. Field workers will be responsible for picking up cups at this timepoint. No visit to the field laboratories will be required. Urine will be collected for CCA/CAA. Blood (7 ml) will be collected for the same subset of N=150 subjects for studies of immunological responses as at baseline.

3. *Study Visit 3 (6 months post enrolment)* Six months (+/- 2 weeks) following visit one, subjects will return to the respective field laboratories. They will receive either the same dose of Praziquantel as received at Visit 1 or placebo as determined at baseline randomization. At this

visit, and before the study drug or placebo is received, blood will be drawn for follow up assessment of morbidity, and in depth measures of nutritional status. An ultrasound scan will be performed. Blood (7 ml) will be collected for the same subset of N=150 subjects for studies of immunological responses. Urine will be stored at this visit for future processing of CAA to monitor re-infection.

4. Study Visit 4, Close out. (12 months post enrollment) Twelve months (+/- 2 weeks) post enrollment and initial treatment, study subjects will return to the field laboratory. Prior to this visit they will be asked to provide three stool samples and one urine. At this visit, blood will be drawn for follow up morbidity studies and in-depth measures of nutritional status will be made. All children will be treated with Praziquantel and those infected with soil-transmitted helminths will be treated with albendazole 200 mg (12 – 24 month old children) or albendazole 400 mg (children over age two). A repeat ultrasound scan will be done before the participant is discharged from the study. If however, the ultrasound scan at six months revealed resolution of any pathology detected at baseline, there will be no repeat at discharge. Blood (7 ml) will be collected for the same subset of N=150 subjects for studies of immunological responses.

